Title: Evaluating values-based motivational interviewing to increase treatment completion with fixed dose combination MK-5172/MK-8742 among Veterans with active substance use disorders and treatment-naïve genotype 1 chronic hepatitis C

Investigators: [name] [name]., [name].,

1. Objective and hypotheses.

Primary Objective: Implement a values-based motivational interviewing (VBMI) intervention to promote treatment completion with fixed dose combination (FDC) MK-5172/MK-8742 (elbasvir/grazoprevir, Zepatier™) x 12 weeks among treatment-naïve Veterans with substance use disorder (SUD) and genotype 1 chronic hepatitis C virus (HCV) infection.

Primary Hypothesis: Veterans with SUD and genotype 1 chronic HCV infection who receive the VBMI intervention will complete the full course of treatment in 90% of cases.

Secondary Objectives:

- 1) Utilize VBMI to promote self-efficacy in taking FDC MK-5172/MK-8742 (elbasvir/grazoprevir, Zepatier™) among Veterans with active SUD and chronic HCV infection.
- 2) Demonstrate the feasibility of FDC MK-5172/MK-8742 (elbasvir/grazoprevir, Zepatier™) for obtaining sustained virologic response (SVR) in treatment-naïve genotype 1 chronic HCV infection among Veterans with active SUD.
- 3) Measure the prevalence of baseline NS5a resistance mutations in Veterans with active SUD and genotype 1a chronic HCV infection. NS5a is a nonstructural HCV protein.

Secondary Hypotheses:

- 1) Veterans with SUD enrolled in this study will demonstrate a trend towards clinically significant increases in HCV treatment adherence self-efficacy scores between baseline and week 4 of treatment.
- 2) FDC MK-5172/MK-8742 (elbasvir/grazoprevir, Zepatier™) will be well-tolerated by Veterans with SUD.

2. Study procedures

2.1 Background: The advent of direct acting antivirals (DAAs) for chronic HCV infection has increased the tolerability and effectiveness of curative HCV treatment. Disorders which can affect adherence to HCV treatment, including SUD, can reduce effectiveness of DAAs. During the pegylated interferon era, the VA HCV 001 study group demonstrated an association

between recent alcohol use and early treatment discontinuation, resulting in decreased treatment efficacy¹. The authors concluded that patients with alcohol use should be provided additional support to assist with treatment completion.

Motivational interviewing (MI) was initially developed to promote abstinence in those with alcohol use disorders². In recent years, the core of MI techniques has been applied to other behavioral areas, including medication adherence³. Prior investigations have determined that MI can promote increased medication adherence among patients with HIV infection³⁻⁴, but less is known about the effect of MI on adherence to HCV medications. One prior study has associated self-efficacy, an idea conceptually linked to MI, with reduced risk of missed HCV medication doses⁵.

Acceptance and Commitment Therapy (ACT) encourages the patient to use mindfulness to promote dedication to behavioral change⁶. The patients accept the difficulties inherent to making the change and develop techniques to manage these difficulties. One major component of ACT is identifying values that make a life worth living and then mindfully moving towards such values. This approach has shown promise with tobacco use disorders⁷ and has been used to promote psychotherapy attendance among substance use disorders⁸.

We hypothesize an intervention which uses VBMI would increase rates of HCV treatment completion with FDC MK-5172/MK-8742 (elbasvir/grazoprevir, Zepatier™) among treatment naïve Veterans with HCV genotype 1 and SUD. MK-5172/MK-8742 (elbasvir/grazoprevir, Zepatier™) is a fixed dose combination once daily oral medication for chronic HCV. In clinical trials, treatment-naïve patients with genotype 1 HCV who received 12 weeks of MK-5172 and MK-8742 had sustained virologic response rates of 98%⁹.

Approximately 1 in 4 Veterans with chronic HCV have an active SUD requiring hospitalization or residential treatment¹⁰. As patients with active SUD are often excluded from clinical trial participation, examining the feasibility of using emerging DAAs in this population is warranted.

2.2 We will conduct a prospective study of **20** Veterans with treatment-naïve genotype 1 chronic hepatitis C infection admitted to the Substance Abuse Residential Rehabilitation Treatment Program (SARRTP) and/or diagnosed with SUD with ICD-10 CM code for in past 6 months. at the G.V. (Sonny) Montgomery VA Medical Center. Institutional Review Board approval will be obtained prior to the conduction of the study.

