The **Medical Outcomes Study Social Support Survey (MOS-SSS)** has also been widely used and validated among persons with chronic medical illness, including Veterans with chronic hepatitis C. This 19-item survey assesses the patients’ perceptions of their existing emotional support, tangible support, affectionate support, and social interactions.

The **Patient Health Questionnaire (PHQ-9)** is a validated survey of depressive symptoms. Higher scores indicate a greater likelihood of clinical depression. This survey is currently used to screen for depression annually in Veterans in care at VA Medical Centers.

The HCV-Treatment Self Efficacy (HCV-TSE) is a standardized survey which assesses self-belief that a patient can complete his/her treatment regimen of pegylated interferon and ribavirin. The patient rates their confidence in their ability to take medications on a scale of 0 to 10, where 0 indicates no confidence and 10 indicates full confidence. The answers to the four individual questions are averaged to a score of 0 to 10. We have adapted 4 questions from the original scale regarding medication adherence (**HCV-TSE-A**) to assess a patient's perceptions of his/her ability to adhere to DAAs.

2.5.5 Follow-up visits:

The study will last 12 weeks, with follow up visits at Weeks 2, 4, 6, 8, 10 and 12, which will be coordinated to occur on the same date as Veterans' substance abuse aftercare visits. Side effects of medications and tolerance of medications will be monitored at each visit using a single question about side effects experienced and response options including the most common side effects and a response of "other" and a description of that side effect. A single question will also be used to assess for any substance use since the last visit, with quantity and frequency being recorded if the response is positive.

Adherence will be assessed at each follow up visit using the Visual Analog Scale and pill counts. Routine laboratory monitoring will include a CBC, CHEM 14, HCV RNA and a urine sample analyzed for cocaine, marijuana, opioid, and amphetamine use (all tests are standard of care). The HCV-TSE-A will be repeated at week 4. Assessments of depressive symptoms (PHQ-9) and health-related quality of life (SF-36) will be repeated at weeks 4 and 12.

If a patient fails to complete the study, a lost to follow up form will be completed,

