Patients will be assigned a unique study number which does not contain PHI. This number will be used on all data collected for the purposes of this study. A master list of subjects which links the study number and patient identifiers will be maintained on an encrypted VA server. The data for this study will be entered into Microsoft Excel 2010. The investigator(s) and their research personnel are responsible for maintaining the study database, which will be kept on an encrypted VA server. No data will be stored on a hard drive of a PC. Only key personnel for this study will have access to the research data and access to this data will be terminated if/when the personnel are removed from the study. Research data will be maintained according to the VA records schedule. Data containing PHI will not leave the VA premises. A contract biostatistician will be used to analyze de-identified study data.

Variables/Time Points of Interest

The primary outcome of interest is the percentage of patients completing 12 weeks of treatment with FDC MK-5172/MK-8742 (elbasvir/grazoprevir, Zepatier™). Treatment completion will be defined as attendance at the last treatment visit (i.e., Week 12). Adherence will be categorized into <90% adherence and ≥ 90% adherence, based on an observed relationship between ribavirin adherence and early virologic response¹¹.

Statistical Methods

Binary logistic regression analysis will be used to report adjusted odds ratios. Differences in the distribution of HSV-TSE-A scores across categorical visits (baseline vs. Week 4) will be assessed using Wilcoxon rank sum test. In addition, parametric models (linear regression) will be explored to estimate the differences.

Power/Sample Size:

In our pilot program of 4 Veterans, we found that 75% completed 12 weeks of treatment. Estimating a 90% (18/20) completion rate in the VBMI arm, we anticipate that a sample size of 20 patients will demonstrate a trend towards higher completion rates with the VBMI intervention. We also anticipate the study will demonstrate a high rate of medication adherence. It is our intention to use data from this study to develop larger protocols with more robust sample sizes.

Limitations:

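### The self-efficacy hypothesis is about the size of a within-patient rise, but the named test gives no size and ignores the pairing, and no important change on the 0-10 scale is defined

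*Combined protocol and SAP*

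**What the plan says.** Section 1, secondary hypothesis 1, states that Veterans in the study "will demonstrate a trend towards clinically significant increases in HCV treatment adherence self-efficacy scores between baseline and week 4 of treatment".

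Section 2.5.4 describes the instrument. For the parent scale, "The answers to the four individual questions are averaged to a score of 0 to 10". That scale was written for pegylated interferon and ribavirin, and for this study the protocol says "We have adapted 4 questions from the original scale regarding medication adherence", giving the HCV-TSE-A. No important difference is given for either version.

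The score is taken at baseline (section 2.5.2), and section 2.5.5 adds "The HCV-TSE-A will be repeated at week 4". Each patient therefore contributes a pair of readings.

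Under Statistical Methods, differences in the score distribution "across categorical visits (baseline vs. Week 4) will be assessed using Wilcoxon rank sum test". The next sentence reads "In addition, parametric models (linear regression) will be explored to estimate the differences". Neither method is called primary. No confidence interval, threshold, responder definition or decision rule is stated for this endpoint. The Power/Sample Size text covers treatment completion and, in words only, adherence.

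**The concern.** The hypothesis asks whether self-efficacy rises by an amount that matters. Three parts of the plan do not fit that question.

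- The one test the plan commits to asks whether two distributions differ. Its p-value depends on the shift relative to the spread, so it cannot say whether a rise is clinically important.
- The rank sum test is for two independent samples. Here the same patients are measured twice, so it discards the within-patient comparison that the hypothesis is about.
- The planned estimate is only exploratory. The plan does not say whether the regression will respect the pairing, promises no interval, and gives no value to set the estimate against.

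At stake is the usefulness of the result. The protocol intends its data to inform larger studies, and for that an estimated change with its uncertainty is worth more than a p-value. Without a stated size, whether a rise was clinically significant would be decided after the data are seen.

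**Working it through.** The plan gives no self-efficacy figure to reproduce: no effect size, SD, alpha or power is stated for this endpoint.

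**Inputs from the protocol.** n = 20 (section 2.2 and Power/Sample Size); score range 0 to 10 (section 2.5.4); two readings per patient (sections 2.5.2 and 2.5.5).

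**Assumptions.** SD of the within-patient change 1 to 3 points; equal SD at both visits; within-patient correlation ρ of 0.5, with other values shown; two-sided 5%; no missing Week 4 scores unless stated; normal data, ignoring the bounds of the scale.

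**Step 1. Does the rank sum p-value track size?** One constructed data set of 20 values per visit was rescaled by 0.25, 1 and 3. The mean rises were 0.11, 0.45 and 1.35 points. All three gave p = 7.1 × 10⁻⁶, because rescaling both visits together leaves the ranks unchanged. The p-value cannot separate a trivial rise from a large one.

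**Step 2. Precision of a paired estimate.** Half-width = t(0.975, 19) × SD of change / √20, with t = 2.093.

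| SD of change | Half-width, points |
|---|---|
| 1.0 | 2.093 × 1.0 / 4.472 = 0.47 |
| 1.5 | 2.093 × 1.5 / 4.472 = 0.70 |
| 2.0 | 2.093 × 2.0 / 4.472 = 0.94 |
| 2.5 | 2.093 × 2.5 / 4.472 = 1.17 |
| 3.0 | 2.093 × 3.0 / 4.472 = 1.40 |

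With 15 evaluable patients (assumed), the range is 0.55 to 1.66 points.

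**Step 3. Precision if the visits are treated as independent.** SD of change = SD per visit × √(2(1 − ρ)), so at ρ = 0.5 the two SDs are equal. Half-width = t(0.975, 38) × SD per visit × √(2/20), with t = 2.024.

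- SD 1.5: 2.024 × 1.5 × 0.3162 = 0.96 points, against 0.70 paired.
- SD 2.0: 2.024 × 2.0 × 0.3162 = 1.28 points, against 0.94 paired.

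The ratio of half-widths is (2.024/2.093)/√(1 − ρ): 0.97 at ρ = 0, 1.16 at 0.3, 1.37 at 0.5 and 1.77 at 0.7. Pairing costs almost nothing if the readings are uncorrelated and gains steadily as correlation rises.

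**Step 4. Behaviour of the named test on paired data.** Simulation, n = 20, shift of 0.5 SD per visit:

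| ρ | Rank sum, true type I error | Rank sum, power | Signed rank, power |
|---|---|---|---|
| 0 | about 5% | 32% | 30% |
| 0.3 | 2.5% | 29% | 41% |
| 0.5 | about 1% | 26-28% | 54-55% |
| 0.7 | 0.1% | 23% | 76% |

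**Step 5. Would a small but consistent rise be declared a success?** Take a 0.3-point rise with SD of change 0.6. From Step 3, ρ = 1 − 0.6²/(2 × SD²), where SD is the between-patient SD at each visit.

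| Between-patient SD | ρ | Rank sum significant |
|---|---|---|
| 0.6 | 0.50 | 27% |
| 1.0 | 0.82 | about 2.5% |
| 1.5 | 0.92 | 0.1% |

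The signed rank test is significant 53 to 55% of the time in all three cases. The named test is therefore more likely to miss such a shift than to report it.

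**The case against.** The best defence is that the plan does provide for an estimate: the sentence after the rank sum test says that linear regression will be explored for that purpose. A reader might infer that a primary test yielding only a p-value leaves the hypothesis unanswerable. The documents do not support that. No test is labelled primary, and a size estimate is planned, though weakly. What is missing is a committed paired estimate, an interval and a value to judge it by.

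A reader might also infer that, under this plan, a small consistent rise would be reported as support. Step 5 shows otherwise: the named test ignores within-patient consistency and would rarely flag such a rise once the between-patient SD is 1 or more.

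The defence can add that the hypothesis claims only a trend, in a small single-group study meant to prepare larger ones, and that no decision about efficacy is shown to hang on it. That stands and lowers the severity. It does not remove the point, because trend is undefined too, and a pilot gains most from an estimate with an interval.

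Finally, no particular threshold can be taken from the documents. They give no SD and no important difference for the adapted four-item score, so any value must come from the investigators with reasons.

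**Conclusion.** The point holds in a limited form. The hypothesis concerns the size of a within-patient rise. The one test the plan commits to gives no size and mishandles the pairing, the estimate is left exploratory without an interval, and no important change on the 0-10 scale is defined.

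The loss is moderate and depends on assumptions. At ρ = 0.5 an analysis that ignores pairing gives an interval about 37% wider, while at zero correlation there is no loss. A paired interval at n = 20 would still span roughly ±0.5 to ±1.4 points for an SD of change from 1 to 3. Better analysis makes the answer interpretable but not precise.

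Severity is low: a hedged secondary hypothesis in a 20-patient pilot, with both readings already planned.

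**What to change.** In Statistical Methods, before analysis:

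- Make the main self-efficacy result the mean within-patient change from baseline to Week 4 (or the median, if the scores are skewed or pile up near 10; choose in advance), with a 95% confidence interval from a paired method.
- Keep a rank test as supportive only. The signed rank test is the version that fits paired readings.
- State how many patients have both scores and how a missing Week 4 score is handled.

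In secondary hypothesis 1, do one of two things. Either state and justify the change on the 0-10 HCV-TSE-A that the investigators regard as clinically important, and report the number of Veterans reaching it with an exact 95% interval. Or drop the words clinically significant and present the change as an estimate.

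The cost is wording in two places: no new visits, patients or data. The downside is that a claim with a stated threshold becomes falsifiable and, with 20 patients, may well not be met.

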2.3.1 Study Population

The G.V. (Sonny) Montgomery VAMC is an urban, academically-affiliated medical center in the Southeastern United States. . The center provides care to approximately 39,000 unique Veterans annually in rural and urban areas of Mississippi and surrounding states. The hepatitis clinics in the facility meet 3 ½ days weekly and, to date, have provided DAAs to over 600 Veterans with chronic HCV. As part of a pilot treatment program, 4 Veterans initiated HCV treatment while in residential treatment for SUD. Of these, 3 completed all 12 weeks of treatment while 1 relapsed into alcohol abuse and was lost to follow up.

The HCV treatment clinics meet 3 ½ days weekly to provide DAA treatment for HCV. Veterans with co-existing MH conditions are frequently seen in clinic, including active SUD. Active SUD is not a contraindication for treatment provided the Veteran demonstrates he/she can adhere to medications and follow up visits. Patients with active SUD who begin DAA treatment as an outpatient are followed every 2 weeks.

Inclusion criteria:

- 1) Identified as having treatment-naïve genotype 1 chronic HCV infection; Veterans who are genotype 1a must have baseline NS5a resistance testing
- 2) Current resident of the SAR RTP program and/or ICD-10 CM code for SUD (F10-F19) within the past 6 months
- 3) Willing to initiate treatment with FDC MK-5172/MK-8742 (elbasvir/grazoprevir, Zepatier™)

Exclusion criteria:

- 1) Contraindications for therapy with FDC MK-5172/MK-8742 (elbasvir/grazoprevir, Zepatier™)
- 2) Unable to provide written informed consent
- 3) Hepatocellular carcinoma or other medical condition precluding HCV treatment
- 4) Acute HCV infection
- 5) Prior treatment for chronic HCV
- 6) History of decompensated cirrhosis
- 7) Platelet count < 75 K/cmm and/or albumin < 3 grams/dL
- 8) Females and male sex partners of females who are pregnant, nursing and/or unwilling to use contraception
- 9) Patients infected with genotype 1a who have not undergone baseline NS5a resistance testing

See attached flow chart.

2.5.1 Participant Recruitment and Enrollment: Veterans with active SUD are regularly screened for chronic HCV infection. All patients with chronic HCV are subsequently referred to the HCV treatment clinic for treatment evaluation. When evaluating a patient for HCV treatment, current diagnoses including SUD (ICD10 CM F10-F19) are routinely noted. It is standard of care for patients who are infected with HCV genotype 1a to undergo baseline resistance testing before initiation with MK-5172/MK-8742 (elbasvir/grazoprevir, Zepatier™). Patients meeting inclusion criteria will be offered study participation at their clinic visit. Basic demographic data (age-if less than 89 years, race, gender) will be recorded on all patients who are asked to participate in the study to allow investigators to assess for enrollment bias. Patients who agree to participate will give their written informed consent. Patients will be assigned a unique study number that does not contain personal identifiers after signing informed consent. Each patient will have only one number for the duration of the study. Study records will be labeled with this unique study number and will not contain PHI. Treatment will be prescribed in accordance with US labeling as described in the package insert.

Genotype 1b: 12 weeks MK-5172/MK-8742 (elbasvir/grazoprevir, Zepatier™)
Genotype 1a without NS5a RAVs: 12 weeks MK-5172/MK-8742 (elbasvir/grazoprevir, Zepatier™)
Genotype 1a with NS5a RAVs: 16 weeks MK-5172-MK-8742 (elbasvir/grazoprevir, Zepatier™) with weight based ribavirin

2.5.2 Baseline visit: Patients will complete a survey of demographic (age, gender, race/ethnicity, income level, marital status, education level, distance from medical center) and medical information. Drug Abuse Screening Test (DAST) and AUDIT will be completed to assess severity of SUD. We will also assess health related quality of life (Rand-36 item Health Survey [Short Form-36]), social support (Medical Outcomes Study Social Support Survey [MOS-SSS]), depressive symptoms (Patient Health Questionnaire [PHQ-9]), and treatment adherence self-efficacy (HCV Treatment Self Efficacy-A [HCV TSE-A]).

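### The expected gain in completion is read against 3 of 4 pilot patients, while the same clinic's records on active-SUD Veterans treated with DAAs go unused

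*Combined protocol and SAP*

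**What the plan says.** The title and section 2.1 present VBMI as a way to raise treatment completion. Under Power/Sample Size the plan states "In our pilot program of 4 Veterans, we found that 75% completed 12 weeks of treatment", continues with "Estimating a 90% (18/20) completion rate in the VBMI arm", and concludes that "a sample size of 20 patients will demonstrate a trend towards higher completion rates with the VBMI intervention". The pilot is described in section 2.3.1: "4 Veterans initiated HCV treatment while in residential treatment for SUD", of whom 3 finished and 1 was lost to follow-up.

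The same section says the hepatitis clinics "have provided DAAs to over 600 Veterans with chronic HCV". It adds "Veterans with co-existing MH conditions are frequently seen in clinic, including active SUD" and "Patients with active SUD who begin DAA treatment as an outpatient are followed every 2 weeks". Study visits (section 2.5.5) are also two weeks apart. Section 2.5.1 says SUD diagnosis codes F10-F19 are routinely recorded when a patient is evaluated for HCV treatment.

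Statistical Methods names no comparator and no reference rate. For patients who decline, only age, race and gender are recorded (section 2.5.1 and Limitations). Nothing in the documents plans to obtain completion from the clinic's earlier patients.

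**The concern.** A claim of higher completion needs a rate to be higher than. The trial has no control group, so that rate must come from outside the 20 patients, and the plan takes it from four people. All four started in residential care, whereas the trial also admits Veterans who qualify only through a SUD code in the past 6 months. For outpatient starters, the clinic's ordinary two-weekly follow-up may by itself support good attendance, and the pilot cannot show how well that care performs.

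Two things are at stake. A good result could not be read as better than what the clinic already achieves. The larger protocols that this study is meant to inform would also inherit a control rate based on four patients, although a better source is described in the protocol itself.

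**Working it through.** **Inputs.** Expected VBMI completion 18/20 and pilot completion 3/4 (Power/Sample Size; section 2.3.1). The number of eligible clinic records, m, is not in the documents. It is assumed to be 30 to 150. The upper value is one quarter of 600, borrowing the general 1-in-4 SUD figure in section 2.1, and is illustrative only. Usual-care completion is assumed to be about 75%, and then varied.

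**1. The plan's own figures.** 18/20 = 90% and 3/4 = 75% reproduce. No alpha, power or test is stated, so N = 20 cannot be re-derived.

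**2. Precision of the pilot rate (Clopper-Pearson).**
- Upper limit: 1 - p^4 = 0.025, so p = 0.975^(1/4) = 0.994.
- Lower limit: 4p^3(1 - p) + p^4 = 0.025, so p = 0.194.
- The interval is 19.4% to 99.4% and contains the 90% target. The interval for 18/20 is 68.3% to 98.8% and contains 75%.

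**3. Can 20 patients be separated from 3/4? (Fisher exact)**
- 18/20: there are 3 non-completers among 24. The chance that at least one falls among the 4 pilot patients is 1 - C(20,3)/C(24,3) = 1 - 1140/2024 = 0.44, which is also the two-sided p.
- 20/20: the single non-completer falls in the pilot group with probability 4/24 = 0.17, the smallest p available for any result above 75%.

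**4. Difference for 18/20 against 3/4 (Newcombe).** The Wilson limits are 69.9% to 97.2% for 18/20 and 30.1% to 95.4% for 3/4.
- Lower: 0.15 - sqrt[(0.900 - 0.699)^2 + (0.954 - 0.750)^2] = -0.137
- Upper: 0.15 + sqrt[(0.972 - 0.900)^2 + (0.750 - 0.301)^2] = +0.605

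**5. The same calculations with clinic records as the reference.**

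| Reference (assumed except 3/4) | Exact 95% CI of reference | 18/20 minus reference, Newcombe 95% CI (points) |
|---|---|---|
| 3/4 (plan) | 19% to 99% | +15 (-14 to +61) |
| 22/30 | 54% to 88% | +17 (-7 to +36) |
| 45/60 | 62% to 85% | +15 (-7 to +29) |
| 75/100 | 65% to 83% | +15 (-6 to +27) |
| 112/150 | 67% to 81% | +15 (-6 to +26) |
| 90/100 | 82% to 95% | 0 (-21 to +10) |

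The last row matters because the 75% is itself the pilot rate. If routine care already achieved 90%, 18/20 would show no gain.

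**6. What the records would not do.** Two-sided 5% power (exact Fisher) for 90% against 75%, with 20 VBMI patients and m = 30 to 150, is 20% to 28%, compared with about 7% for m = 4. Beyond a modest number of records, the 20 VBMI patients set the limit.

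**The case against.** The strongest reply is that this is a pilot. Its primary objective is to implement VBMI, its primary hypothesis is an absolute 90%, and the plan promises only a trend. A rate with its confidence interval would meet that aim, and dropping the word higher would remove the inconsistency without a second cohort. This stands as an alternative and limits how serious the point is. It does not answer the need for a control rate in the later protocols.

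A reader might infer that the trial has no usual-care reference at all. The documents do not support that: the pilot figure is cited and set against 90%. It is inadequate, not absent.

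A reader might also infer that over 600 comparable controls are waiting in the files. That count covers every Veteran given DAAs. How many had active SUD, genotype 1, no previous treatment and a 12-week course is not stated. Two-weekly follow-up is stated only for outpatient starters, and the absence of VBMI from routine care is a reasonable inference that no section confirms.

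Routine patients with active SUD were treated only if they showed that they could adhere to medication and visits. The trial's inclusion criteria do not list this condition. If it does not apply to trial patients, the historical rate may be too favourable.

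The pilot's outcome is worded as completing treatment and the trial's as Week 12 attendance, but this carries little weight: the one pilot non-completer was lost to follow-up, so 3/4 probably holds under either wording.

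**Conclusion.** The point holds as a gap in the benchmark. The plan makes a comparative claim whose only reference has a 95% CI of 19% to 99%, so that no favourable result, including 20/20 (p = 0.17), can be told apart from it. A better source is described in the same document and not used. On the assumption of 30 to 150 eligible records at about 75% completion, the interval for the difference shrinks from 75 points wide (-14 to +61) to between 43 (-7 to +36) and 32 (-6 to +26). With 18/20 it still includes zero, so it would be wrong to read this as a route to a significance test. The gain is a readable descriptive reference and a more credible control rate. The record count and the 75% are assumptions; the direction of the improvement does not depend on either, but its size does. This is a worthwhile, inexpensive improvement and not a flaw that invalidates the study.

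**What to change.** Add to Statistical Methods a descriptive reference group drawn from the clinic's records: treatment-naive genotype 1 Veterans who met the study's SUD criterion and started a 12-week DAA course at this clinic in a fixed period before enrolment opened. Then:

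- Apply the trial's completion definition, attendance at the Week 12 visit, to both groups.
- Report the number of eligible records, the reference rate with an exact 95% CI, and the difference from the VBMI group with a Newcombe 95% CI, overall and by residential versus outpatient start.
- Use this rate in place of 3/4 as the benchmark and as the control rate for the larger protocol.
- State that the comparison is non-randomised and not powered; that regimen and calendar time differ; that routine care is assumed not to have included VBMI; and that routine patients with active SUD had first to demonstrate adherence, which may raise the reference rate.

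If the extraction is not feasible, report the VBMI rate with its CI and remove the claim of higher completion.

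The cost is a records extraction and IRB approval for retrospective data. No new patients or visits are needed, and treatment does not change. The downside is residual confounding, which the stated caveats disclose but do not remove.
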